**Study Design**

1. Prospective, parallel clinical trial
2. Participants will be tested at enrollment (2 weeks after ACLR or when 50% weightbearing is allowed) and again after completing the study intervention at 3 months and 6 months post ACLR.

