**BEGINNING KINEMATIC SAMPLE RATE = 120 Hz**

1. Standing Calibration (named sc)
2. Self-selected walking speed (3, 6 months)
  - a. 8 trials collected on each limb (named walk01, etc.)
3. Bilateral squats (eyes open, arms folded across chest, re-do trial if balance is lost) (2 weeks & 3, 6 months)
  - a. 1 trial = 5 squats
  - b. 1 practice, 3 collected trials of max squats (named bilsquatmax01, etc.)
  - c. **Metronome: 3 seconds down, 3 seconds up**
    - i. **Verbal cues: “Down, 2, 3, Up, 2, 3”**
  - d. Pain is only to increase by 2/10 from pain in standing; either 1) modify depth of squats or foot position or 2) omit the testing (if unable to test involved max squats, still completed unininvolved max squats)

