## Statistical Analysis Plan

### **Data analysis plan:**

A p-value less than 0.05 will be considered statistically significant unless otherwise specified.

To determine the efficacy of the visual biofeedback program, analyses of covariance (ANCOVA) will be used at 3 and 6 months after ACLR to test differences in the interlimb ratio (ILR = injured limb / uninjured limb) of the knee flexion moment impulse during squatting, after adjusting for baseline knee flexion moment impulse. An ANCOVA will also be used to test differences in the ILR of the vertical ground reaction force impulse.

Independent t-tests will be used to test the percent change in cartilage T2 relaxation time in the injured knee from 2 weeks to 6 months after ACLR between groups, quadriceps strength, and gait biomechanics. For quadriceps strength, limb symmetry indexes will be computed (LSI = injured limb / uninjured limb x 100%).

If assumptions for any of these tests are violated, a nonparametric test will be conducted.

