### **Sample size analysis:**

Using our preliminary data, a sample size of 20 (10 per group) achieves 82.5% power to detect a difference in the knee flexion moment (KFM) impulse ILR of 0.283 during squats between the biofeedback (expected ILR=0.800±0.183) and standard of care group ( expected ILR=0.517±0.228) using a two-sided hypothesis test and p-value of 0.05. Group differences are based on our preliminary data after standard of care: KFM impulse ILR at 4 months (N=20): 0.517±0.228; KFM impulse ILR at 10 months (N=5): 0.971±0.183. Thus, our expected KFM impulse ILR for the biofeedback group at 3 and 6 months is 0.800±0.183. To test our hypothesis that the biofeedback group will walk with a greater KFM than the standard of care group, the minimal detectable change (MDC) of 0.09 N·m/kg·m with a standard deviation of 0.08 was used (Gardinier 2013). Using this expected group difference, a sample size of 28 (14 per group) achieves 81.7% power using a two-sized hypothesis test and p-value of 0.05. To account for 10% attrition, 32 participants will be enrolled.

A sample size of 30 (15 per group) achieves 81.0% power to detect a group difference of  $2.9 \pm 2.7$  milliseconds in T2 relaxation time (primary outcome; measured from 2 weeks to 6 months in the injured knee). This expected group difference is based on a change in T2 relaxation time of  $2.9 \pm 2.7$  milliseconds in the medial femoral cartilage by 6 months after ACLR as reported by Kumar et al. Preliminary data of 37 participants from our ongoing NIH R21 study indicate that quadriceps strength LSI following standard care is  $66.0 \pm 21.1\%$  at 6 months after ACLR. The evidence-based clinical targets for quadriceps strength at 6 months is 90.0%. Using the expected quadriceps strength LSI of 66.0% in the control group and 90.0% in the intervention group at 6 months after ACLR with a pooled standard deviation of 21.1%, a sample size of 30 (15 per group) achieves 91.8% power using a two-sided hypothesis. To account for attrition, 34 participants will be enrolled.

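### The SAP has no rule for an omitted baseline squat test, so the squat ANCOVAs would drop participants whose 3- or 6-month outcome was observed

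*Combined protocol and SAP*

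**What the plan says.** The data analysis plan states that "analyses of covariance (ANCOVA) will be used at 3 and 6 months after ACLR" for the knee flexion moment impulse, expressed as an "interlimb ratio (ILR = injured limb / uninjured limb"), "during squatting, after adjusting for baseline knee flexion moment impulse". It does not say whether the covariate is the ratio or a single-limb value. For the second squat outcome it says "An ANCOVA will also be used to test differences in the ILR of the vertical ground reaction force impulse", naming no covariate.

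Under Study Design, "Participants will be tested at enrollment (2 weeks after ACLR or when 50% weightbearing is allowed"), then at 3 and 6 months. The bilateral squat item under Biomechanical Testing applies to all three sessions. Its pain rule is triggered by a rise in pain above the level in standing, and staff then "either 1) modify depth of squats or foot position or 2) omit the testing". The same rule foresees a session in which only the uninvolved side is tested, which leaves no ratio.

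The SAP gives no missing-data method, no rule for a missing covariate and no analysis population. The only data-inclusion rules, in the Progression Plan and the Modifications table, concern attendance at training sessions.

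**The concern.** The baseline squat test is the one closest to surgery, and the protocol itself provides for it to be skipped. A model that adjusts for baseline cannot use a record with no baseline value unless something is put in its place. A participant could attend every visit, complete the training and squat at 3 and 6 months, yet contribute to neither squat analysis because one covariate is blank.

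In a trial of 34, each observed outcome is worth keeping. Discarding some costs precision, and those retained would be the ones who could do the early test.

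**Working it through.** **Inputs from the documents (Sample size analysis).** Expected ratio 0.800 (SD 0.183) with biofeedback and 0.517 (SD 0.228) with standard care; difference 0.283; two-sided 0.05; 10 per group for 82.5% power; 30 evaluable and 34 enrolled in the largest calculation.

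**Assumptions (not in the documents).** Share of omitted baselines π = 10% or 20%, unrelated to outcome or group. Correlation ρ between baseline and outcome = 0.3, 0.5 or 0.7. Fifteen per arm with follow-up.

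**Step 1: reproduce the plan's figure.** Pooled SD = √[(0.183² + 0.228²)/2] = 0.2067. Noncentrality = (0.283/0.2067) × √(n/2). With n = 10 this is 1.369 × 2.236 = 3.06 on 18 degrees of freedom, giving power of 82.5%, as stated.

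**Step 2: power after case deletion.** Same formula, no credit for the covariate, equal split assumed:

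- 30 analysed (15 per arm): 1.369 × √7.5 = 3.75, power 95.1%.
- 27 analysed (10% omitted, 13.5 per arm on average): 1.369 × √6.75 = 3.56, power 92.7%.
- 24 analysed (20% omitted, 12 per arm): 1.369 × √6 = 3.35, power 89.3%.

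**Step 3: variance against keeping everyone.** Case deletion leaves a fraction 1 − π of the sample, with residual variance proportional to 1 − ρ². Filling with the pooled mean keeps the whole sample, but the covariate then explains only ρ²(1 − π). In large samples the variance ratio, deletion over filling, is

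(1 − ρ²) / {(1 − π) × [1 − ρ²(1 − π)]}.

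- π = 10%: ρ = 0.3, 0.91/(0.9 × 0.919) = 1.10; ρ = 0.5, 0.75/(0.9 × 0.775) = 1.08; ρ = 0.7, 0.51/(0.9 × 0.559) = 1.01.
- π = 20%: ρ = 0.3, 0.91/(0.8 × 0.928) = 1.23; ρ = 0.5, 0.75/(0.8 × 0.80) = 1.17; ρ = 0.7, 0.51/(0.8 × 0.608) = 1.05.

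Simulation at 15 per arm (difference 0.283, SD 0.2067, 8,000 trials per cell) gave 1.10, 1.08, 1.02 at 10% and 1.26, 1.19, 1.04 at 20%. Repeat runs stayed within 1.01–1.11 and 1.04–1.27. At the upper end the standard error is √1.11 = 1.05 or √1.27 = 1.13 times as large. Both methods were unbiased under random omission.

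**Step 4: omission linked to pain (illustration).** Thirty participants, ρ = 0.5, 20% omitted in the most painful knees, 4,000 trials. With the same effect in everyone, deletion gave a mean estimate of 0.285 for a true 0.283. Power was 95% with deletion, 98% with mean filling plus a missing-value indicator, and 99% had no baseline been lost.

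**The case against.** The SAP never says it will delete cases; deletion is how ANCOVA behaves when a covariate is blank and the plan is silent. That silence is the gap, so the point stands, but several stronger readings do not.

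- A reader might infer that the most painful knees lose their results. The rule lists modifying the squat before omitting it, and its trigger is a rise over standing pain, not pain itself. Baseline is also deferred until 50% weightbearing is allowed. No omission rate is given.
- A reader might infer a biased comparison. Step 4 shows none under a uniform effect. If the effect is assumed to shrink by 0.10 per SD of pain, deletion gives 0.319 against a true average of 0.283, and keeping everyone gives 0.287. Nothing in the documents supports that slope. Independence of omission from group is not assured either, since Recruitment & Patient Tracking lists group assignment before the scheduling of tests; but no imbalance is shown.
- A reader might cite "To account for 10% attrition, 32 participants will be enrolled" as too thin an allowance. That sentence belongs to the gait calculation, which needs 28. The squat calculation needs 20 and enrolment is 34, a margin of 14 that absorbs dropout and missing covariates alike.
- A reader might say that separate ANCOVAs ignore the 3-month value of someone who misses 6 months. The 3-month ANCOVA uses it; only the 6-month analysis does not borrow from it. That is an accepted choice.

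T2 relaxation time, which the sample size section labels primary, does not use the squat baseline. Nor do the strength and gait t-tests.

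**Conclusion.** The gap is real and its effect modest. With 10% or 20% of baselines omitted at random among 30 participants, dropping those cases inflates the variance of the group effect by about 1–11% or 4–27% relative to pooled-mean filling, with the larger figures at the weaker correlation. Unadjusted power stays at about 93% or 89%, above the 82.5% planned. The analysed group may also shift toward participants who tolerated the early squat test, by an amount the documents do not allow one to estimate. Neither an underpowered squat analysis nor a biased comparison follows. These figures rest on the assumed omission rates and correlations, and on omission being unrelated to group. The knee flexion moment analysis is clearly affected; the ground reaction force analysis is affected only if it adjusts for its own squat baseline.

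**What to change.** Keep the ANCOVAs and add to the SAP, before outcome data are examined:

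1. The covariate in each squat ANCOVA is the baseline value of the same ratio as the outcome.
2. A missing baseline is replaced by the mean of the observed baselines across both groups, so that every observed 3- or 6-month outcome is analysed.
3. Omitted and modified baseline squat tests are counted and reported by group. Modified tests yield a value, but under different conditions.

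An acceptable alternative is one constrained longitudinal model per squat outcome (common baseline mean, group-by-visit terms, unstructured covariance, small-sample degrees of freedom), with the 3- and 6-month contrasts read from it. The figures above do not evaluate that model. Both routes rely on random allocation and on a baseline taken before the intervention starts, so the SAP should state both conditions; the protocol has randomization in a section heading, but its recruitment steps say only that participants are assigned to a group.

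The cost is SAP wording and a little analysis work. No new data are needed, and the clinical pain rule is unchanged.

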**Sample Size and Randomization**

1. N=34 (17 in squat biofeedback group and 17 in control group)
  - a. Target equal number of women and men

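### The 81.0% power for T2, the only outcome labelled primary, is for a difference in milliseconds, but the planned test is on percent change, for which no effect or SD is given

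*Combined protocol and SAP*

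**What the plan says.** Two sections of the Statistical Analysis Plan deal with T2.

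- **Sample size analysis.** The power statement for T2 opens with "A sample size of 30 (15 per group) achieves 81.0% power to detect a group difference of"; the figures given next are 2.9 ± 2.7. Their unit and the status of the outcome then appear as "milliseconds in T2 relaxation time (primary outcome; measured from 2 weeks to 6 months in the injured knee". This is the only place where any outcome is called primary. The effect is taken from a published result in medial femoral cartilage at 6 months, with the same mean and SD: "This expected group difference is based on a change in T2 relaxation time of".
- **Data analysis plan.** The planned T2 comparison, for the interval between the 2-week and 6-month visits, reads: "Independent t-tests will be used to test the percent change in cartilage T2 relaxation time in the injured knee". The significance rule is "A p-value less than 0.05 will be considered statistically significant unless otherwise specified".

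The same Data analysis plan handles squat mechanics differently, by ANCOVA "after adjusting for baseline knee flexion moment impulse". Enrolment, under Sample Size and Randomization, is "N=34 (17 in squat biofeedback group and 17 in control group".

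No T2 effect or SD in percent is given, and no baseline T2 mean or SD. The percentages used as effects and SDs in the sample size text (66.0%, 90.0%, 21.1%) belong to the quadriceps limb symmetry index.

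**The concern.** The trial is sized on one quantity and its primary outcome is tested on another. A difference of 2.9 ms has no fixed equivalent in percent, because each patient's change is divided by that patient's own baseline. The percent-scale SD therefore depends on how much baseline T2 varies and on how baseline relates to change. If the T2 result is null, a reader will want to know whether the planned effect has been excluded. The result will be in percent and the planned effect is in milliseconds, so the plan as written does not answer that.

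A second point concerns efficiency and is not part of the mismatch. Baseline T2 has to be measured to form the percent change, but it is used only as a divisor. The plan already uses baseline-adjusted ANCOVA for squat mechanics.

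**Working it through.** **1. Reproduce the stated power.** Inputs from the Sample size analysis: difference 2.9 ms, SD 2.7 ms, 15 per group. Alpha is 0.05. The T2 sentence does not state sidedness; the knee-moment calculation in the same section is done "using a two-sided hypothesis test and p-value of 0.05", and two-sided is used here.

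- Standard error = 2.7 × √(2/15) = 0.986 ms
- Noncentrality = 2.9 / 0.986 = 2.941, with 28 df
- Power from the noncentral t = **81.04%**, against 81.0% stated

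A one-sided t-test would give 89.0% and a normal approximation 83.7%, so the plan's figure is a two-sided t-test in milliseconds. The same formula gives 83.6% at 16 per group and 85.9% at the enrolled 17.

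**2. Convert to percent.** If every patient had the same baseline B, the difference and the SD would both be divided by B and power would stay at 81%. At B = 45 to 35 ms, 2.9 ± 2.7 ms becomes 6.4–8.3% ± 6.0–7.7%. Baselines differ between patients, so the percent SD is not simply 2.7/B, and power is sensitive to it. With B = 40 ms the difference is 2.9/40 = 7.25%; at 15 per group, power is 89% if the percent SD is 6, 78% if it is 7 and 67% if it is 8.

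**3. Range for the planned test.** The inputs here are assumptions, not figures from the documents: baseline mean 35–45 ms; correlation r between baseline and 6 months; k = 6-month SD / baseline SD, from 0.8 to 1.25; and 2.7 ms taken as the SD of change, so that baseline SD = 2.7 / √(1 + k² − 2rk). Simulated power of the percent-change t-test at 15 per group (40,000 trials per cell):

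| Mean changes | r 0.3–0.8 | r 0.9–0.95 (baseline SD about 5–8.5 ms) |
|---|---|---|
| Control +2.9 ms, biofeedback 0 | 76–81% | 66–82% |
| Control 0, biofeedback −2.9 ms | 80–83% | 74–83% |

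In the first scenario with r 0.3–0.8, power is 79–84% at 16 per group and 81–86% at 17.

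A second grid used other assumptions: baseline mean 30–50 ms, baseline SD 0–6 ms, correlation of baseline with change from 0 to −0.5, and mean changes of 2.9 versus 0 or 5.8 versus 2.9 ms. It gave about 61–81% at 15 per group. The lowest value needs mean 30, SD 6, correlation −0.5 and both groups rising.

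**4. Efficiency of ANCOVA in ms.** Residual variance is k² × (baseline SD)² × (1 − r²), with 2n − 3 df and a variance factor of 1 + 1/(2n − 4). Example with k = 1, r = 0.5, n = 15 per group:

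- Baseline SD = 2.7 / √1 = 2.7 ms
- Residual SD = 2.7 × √0.75 = 2.338 ms
- Standard error = 2.338 × √(2/15 × (1 + 1/26)) = 0.870 ms
- Noncentrality = 2.9 / 0.870 = 3.333, with 27 df; power 89.5%

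| k | r 0.3 | 0.5 | 0.7 | 0.8 | 0.9 | 0.95 |
|---|---|---|---|---|---|---|
| 0.8 | 97.5% | 95.7% | 94.0% | 93.5% | 94.6% | 97.1% |
| 1 | 93.2% | 89.5% | 85.5% | 83.5% | 81.5% | 80.5% |
| 1.25 | 88.1% | 83.8% | 80.2% | 79.5% | 81.5% | 87.0% |

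ANCOVA minus the percent-change test, r 0.3–0.8, both scenarios of step 3: +11 to +20 points (k = 0.8), +2 to +14 (k = 1), −1 to +9 (k = 1.25). If percent change is truly unrelated to baseline, ANCOVA is 1.4 to 2.5 points behind. Type I error was 4.8–5.1% for the percent-change test, the ms-change test and ANCOVA.

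**The case against.** The strongest reply is that little is at stake. Both sections describe the same knee, the same interval and the same two-group comparison, and only the normalisation differs. Over the middle range of assumptions the percent-change test has power close to the stated 81.0%, and 81–86% if all 17 per group are analysed. Percent change is a legitimate prespecified measure, and anyone who supplies a baseline mean can convert 2.9 ms roughly. Using ANCOVA for squat mechanics does not oblige the sponsor to use it for T2, and its gain rests on inputs that the documents do not give. The largest gains appear only if the spread of T2 is smaller at 6 months than at baseline, which nothing in the plan supports.

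Most of this stands as a limit on severity. It does not remove the mismatch: the baseline mean needed for even a rough conversion is absent, and the two grids give different lower ends (66% and 61%), which shows that the planned test's power cannot be fixed from the documents. The point about ANCOVA also stands in part. It is an option that usually helps under the stated assumptions, and restating the calculation in percent would close the mismatch without it.

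**Conclusion.** The concern holds. The 81.0% is arithmetically right for a millisecond difference and is not the power of the percent-change test that the plan specifies for its labelled primary outcome. That follows from the two sections alone and needs no assumption. How far true power departs from 81.0% is unknown. Under assumed baselines it ranges from about the same to several points lower in ordinary cases, and into the 60s only where baseline spread is wide or the mean changes are less favourable. Nothing here shows serious underpowering, and the planned t-test is valid. This should be corrected, but it does not put the trial in doubt.

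**What to change.** Before group data are seen, choose one scale and use it in both sections.

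- **Preferred.** Primary analysis of T2: ANCOVA of 6-month injured-knee T2 (ms) on group, with baseline injured-knee T2 as covariate, reporting the adjusted group difference in ms with its 95% CI. Percent change becomes secondary. Name the cartilage region. The sample size rests on medial femoral cartilage, while the Data analysis plan says only cartilage; tying the two together is sensible, although the scale correction does not depend on it.
- **Alternative.** Keep percent change as the primary test and restate the sample size on that scale: the expected percent difference, its SD with the source, and the resulting power.

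Either closes the mismatch; the first also adjusts for a baseline value that is already collected. The cost is SAP text only, with no new data or visits. ANCOVA uses one degree of freedom and, in unfavourable cases, gives up about 1 to 2.5 points of power. The alternative needs one sentence with a percent-scale effect and SD.

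### T2, the outcome labelled primary, is tested without baseline adjustment although every analysed participant has a 2-week value; an ANCOVA in milliseconds would usually be more precise at almost no cost.

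*Combined protocol and SAP*

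**What the plan says.** The Sample size analysis gives T2 relaxation time the label "primary outcome; measured from 2 weeks to 6 months in the injured knee". Its power statement reads "A sample size of 30 (15 per group) achieves 81.0% power to detect a group difference of" 2.9 ms, with an SD of 2.7 ms.

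The Data analysis plan then states "Independent t-tests will be used to test the percent change in cartilage T2 relaxation time in the injured knee", and the same sentence continues "from 2 weeks to 6 months after ACLR between groups, quadriceps strength, and gait biomechanics". It names no covariate for T2. The preceding paragraph analyses the squat knee flexion moment ratio by ANCOVA, "after adjusting for baseline knee flexion moment impulse".

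No other section adds a baseline-adjusted T2 analysis. The only fallback is a nonparametric test if assumptions fail.

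**The concern.** The plan already uses baseline adjustment, but not for the outcome it calls primary. Percent change cannot be computed without the 2-week scan, so everyone in the T2 comparison already has the covariate.

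A change score depends on baseline: knees that start high tend to rise less, and knees that start low tend to rise more. Percent change does not remove this, and dividing by baseline adds slightly to it. Two things are at stake:

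- **Precision.** Of the four planned powers (82.5, 81.7, 81.0 and 91.8%), T2 has the lowest.
- **Sensitivity to the draw.** With about 15 per arm and no stratification on baseline T2 described, a chance difference between arms at 2 weeks carries into the estimated effect.

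**Working it through.** **Inputs from the documents.** Difference 2.9 ms, change SD 2.7 ms and 15 per group (Sample size analysis); significance level 0.05 (Data analysis plan). The T2 sentence does not state sidedness. Two-sided is stated for other calculations in that section, and it reproduces the T2 figure.

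**Inputs assumed.** The correlation ρ between 2-week and 6-month T2 (shown as a range), equal SDs at the two visits, and a mean T2 of 45 ms for percent change only.

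**Step 1: the plan's own figure.** The standard error is 2.7 × √(2/15) = 0.986 ms and the noncentrality is 2.9 / 0.986 = 2.94. A two-sided t-test on 28 df has 81.0% power, as stated. A one-sided test would give 89.0%. The stated figure is therefore an unadjusted, two-sided t-test on millisecond change.

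**Step 2: ANCOVA at the same sample size.** If the SD at each visit is σ, the change SD is σ√(2(1−ρ)), so σ = 2.7 / √(2(1−ρ)). The ANCOVA residual SD is σ√(1−ρ²) = 2.7√((1+ρ)/2). Estimating the slope multiplies the variance by 1 + 1/(N−4) = 1 + 1/26, and the df are N−3 = 27. Relative to the change score, the variance ratio is ((1+ρ)/2) × (27/26).

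**Step 3: imbalance.** A baseline difference of d ms between arms moves a millisecond-change estimate by (1−ρ)d in the opposite direction. One standard error of baseline imbalance is σ√(2/15).

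| ρ | σ (ms) | Variance ratio | ANCOVA power | Shift per 1 ms imbalance (ms) | One-SE imbalance (ms) | Carried into change (ms) |
|---|---|---|---|---|---|---|
| 0.3 | 2.28 | 0.68 | 93.2% | 0.70 | 0.83 | 0.58 |
| 0.5 | 2.70 | 0.78 | 89.5% | 0.50 | 0.99 | 0.49 |
| 0.7 | 3.49 | 0.88 | 85.5% | 0.30 | 1.27 | 0.38 |
| 0.8 | 4.27 | 0.94 | 83.5% | 0.20 | 1.56 | 0.31 |
| 0.9 | 6.04 | 0.99 | 81.5% | 0.10 | 2.20 | 0.22 |
| 0.95 | 8.54 | 1.01 | 80.5% | 0.05 | 3.12 | 0.16 |

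Omitting the slope term would overstate ANCOVA power by about one point (90.5% at 0.5 and 84.8% at 0.8). For ρ from 0.3 to 0.9, a one-SE imbalance carries 0.58/2.9 = 20% down to 0.22/2.9 = 8% of the target difference into the change estimate.

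**Step 4: the test actually planned.** Percent change was simulated with a mean of 45 ms, one arm rising by 2.9 ms and the other unchanged. Power is about 80, 80, 79, 79 and 78% at ρ 0.3, 0.5, 0.7, 0.8 and 0.9, and about 77% at 0.95, to within about a point. Per 1 ms of imbalance the estimate shifts by 0.74 ms (ρ 0.3) down to 0.14 ms (ρ 0.9), after conversion to milliseconds at 45 ms. Under ANCOVA the shift is about 0. Type I error is near 5% for all three methods.

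**Step 5: scale separated from adjustment.** Against unadjusted millisecond change (81.0%), adjustment alone gains 12.2, 8.5, 4.5, 2.5 and 0.5 points at ρ 0.3, 0.5, 0.7, 0.8 and 0.9. It breaks even at about 0.92 and costs about half a point at 0.95. The rest of the gap from the planned test comes from the percent scale and depends on the scenario in Step 4. If instead the control arm stays flat and the other arm falls, the percent penalty largely disappears, but ANCOVA is still not behind.

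**The case against.** The planned t-test is prespecified and valid, and its millisecond version reaches the stated power at the planned sample size. Every estimate of gain rests on quantities the documents do not give. If ρ is high, adjustment buys almost nothing, and above about 0.92 it costs a little. All of that stands, and it limits the point to efficiency.

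Three stronger readings are tempting, and the documents do not support them:

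- **That the T2 comparison is biased or its error rate inflated.** Under random assignment, chance imbalance averages out and the t-test's standard error already covers it. The dependence on baseline is imprecision in the individual trial, and the same loss that appears in the power figures, so it should not be counted twice. The protocol mentions randomization in a section heading and elsewhere says only that staff assign participants to a group. Both the t-test and the zero shift under ANCOVA rely on that assignment being random; ANCOVA also relies on a roughly linear baseline slope.
- **That the planned test is the least efficient available.** A t-test on 6-month T2 alone would have 59.5, 43.5 and 24.6% power at ρ 0.7, 0.8 and 0.9. It beats the change score only when ρ is below about 0.5.
- **That every enrolled participant will have the covariate.** The eligibility section takes participants who become pregnant out of the MRI portion. The statement is exact only for those in the T2 analysis, which is all the fix needs.

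**Conclusion.** The point holds as a recommendation on efficiency and robustness. The outcome labelled primary lacks a baseline adjustment that the plan applies to the squat outcome and that needs no extra data. With equal SDs, a change SD of 2.7 ms and 15 per arm, ANCOVA does better than the planned percent-change test at every correlation examined. Its advantage over unadjusted millisecond change is material only at moderate correlations. The absence of the covariate is certain; the size of the benefit is not, because ρ and mean T2 are assumptions.

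A reader might infer that the sample size is wrong or that the trial's conclusion would be unsound. Neither follows: the 81.0% is correct for the test it describes, and no increase in enrolment is needed. The change should be made, but the plan is not invalid without it.

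**What to change.** Replace the T2 t-test in the Data analysis plan with an ANCOVA of 6-month T2 (ms) on group and 2-week T2 (ms). Report the adjusted group difference and its 95% CI in milliseconds. Give percent change by arm as description only. This also puts the analysis on the scale of the power statement; moving to millisecond change alone would settle the scale but leave the (1−ρ) dependence on baseline.

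The 81.0% can stay if it is described as the power of the unadjusted millisecond comparison. If an ANCOVA figure is quoted, state the assumed correlation.

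The cost is one SAP sentence and one residual degree of freedom, with no new data. Make the change before outcome data are seen, so that the choice to adjust cannot look data-driven.
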